7.1.3 Linear Regression (LinR)

Quantitative exploratory will be analyzed using linear regression (LinR), and adjusting for participant age group, sex, and WHO COVID ordinal severity at baseline. The effect of the active drug versus placebo will be presented using a difference in means. The difference in means will be presented with 95% credible interval. A flat prior distribution will be used for all model parameters. The posterior distribution for the difference in means will be approximated using the Laplace method. All statistical inferences about the difference in means will be made using this method. Graphical regression diagnostics, including normal Q-Q plots, will be used to assess for severe violations of the linear regression assumptions. Missing exploratory outcomes will be omitted from linear regression analyses.

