### ***Blood collection times (4 total timepoints):***

- Baseline—at time of randomization (Study Day 0).
- Two time points on study drug (Study Day 1  $\pm$  1 day and Study Day 3  $\pm$  1 day)
- Within 2-36 hours after inpatient study treatment ends (or any time on Study Day 5 + 36 hours for final blood collection in the Fostamatinib arm for those still hospitalized at Day 5)

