3.4 Exploratory Outcomes

Exploratory outcomes will include (at least) the following:

Description	Type	Analysis Method
Change in troponin during hospitalization	Quantitative	LinR
Change in NT-proBNP	Quantitative	LinR
Change in RAAS mechanistic biomarkers: 1. AngII 2. Ang(1-7) 3. Plasma renin activity 4. Aldosterone 5. ACE 6. ACE2	Quantitative	LinR
Change in serum creatinine	Quantitative	LinR
Change in eGFR	Quantitative	LinR
Acute kidney injury (KDIGO criteria)	Ordinal	POLR

LinR – Linear Regression; POLR – Proportional Odds Logistic Regression

Exploratory outcomes may be collected at just a subset of sites.

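### Biomarker changes are modelled as untransformed mean differences from a single undefined change, with missing values dropped; a log-scale repeated-measures model would be more precise and less exposed to discharge

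*SAP*

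**What the plan says.** SAP 3.4 lists "Change in troponin during hospitalization", "Change in NT-proBNP" and "Change in RAAS mechanistic biomarkers" (AngII, Ang(1-7), plasma renin activity, aldosterone, ACE, ACE2) as quantitative outcomes analysed by linear regression. SAP 7.1.3 then fixes four things:

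- Effect measure: "The effect of the active drug versus placebo will be presented using a difference in means".
- Covariates: "adjusting for participant age group, sex, and WHO COVID ordinal severity at baseline". The baseline value of the marker is not among them.
- Model checking: "Graphical regression diagnostics, including normal Q-Q plots, will be used to assess for severe violations of the linear regression assumptions". Nothing is said about what follows if they show such a violation.
- Missing data: "Missing exploratory outcomes will be omitted from linear regression analyses".

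Neither section names a measurement scale or the follow-up day that defines the change. Protocol Appendix C schedules four blood collections: baseline, Day 1, Day 3, and one after inpatient treatment ends. For fostamatinib the last is a "final blood collection in the Fostamatinib arm for those still hospitalized at Day 5". Protocol 5.3.3 describes troponin and NT-proBNP before, during and after therapy, and also lists biomarker trajectories.

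SAP 1.1 announces a separate plan for the AngioNECTAR sub-study of renin-angiotensin biomarkers. That plan is not among the documents. SAP 5 and 7.1.4 exclude formal tests of exploratory outcomes.

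**The concern.** Two features of the plan could weaken these readouts.

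**Scale.** With no transformation named, the natural reading is a difference in assay units. Protocol 3.3 describes a mixed population in which up to 20% of COVID-19 patients develop myocardial injury. If the markers are right-skewed in such a population, a few large values dominate the variance of an untransformed change. Because no action follows from a failed Q-Q plot, the scale could end up being chosen after the data are seen.

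**Selection.** A single change uses one follow-up value per participant. If that value is the last sample, a participant discharged before Day 5 has none and is omitted. Staying in hospital is a post-randomisation state that an effective drug can alter. The sampled active group could then be sicker than the sampled placebo group.

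At stake are the width and, to a lesser degree, the fairness of the platform's mechanistic and cardiac comparisons.

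**Working it through.** The documents give no SD, expected change, subset size or missing-data rate for any marker, so there is no planned figure to reproduce. What follows is illustrative.

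**Inputs.** From the SAP: about 300 per group (6.6), which is a ceiling because only some sites may collect these outcomes (3.4), and an odds ratio of 1.65, borrowed from the primary-outcome power statement as an assumed drug effect on discharge. Assumed: log-normal marker with median 1; log-SD s = 0.5, 1.0 or 1.5; baseline to follow-up correlation r = 0.7 on the log scale; true 20% reduction; two-sided 5%. Age, sex and WHO score were left out.

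**Precision, log change.** SE = s × √[2(1−r)] × √(2/n).

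- s = 1.0, n = 300: SE = 0.775 × 0.0816 = 0.063; z = ln(0.8)/SE = −0.223/0.063 = −3.53; power Φ(3.53 − 1.96) = 0.94.
- s = 1.5, n = 300: SE = 0.095; z = −2.35; power 0.65.

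**Precision, untransformed change.** Let V = exp(2s²) − exp(s²) and C = exp(s²)[exp(rs²) − 1]. The change has variance 2(V − C) on placebo and 0.64V + V − 1.6C on active. The mean difference is −0.2·exp(s²/2).

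- s = 1.0: V = 4.67, C = 2.76; variances 3.83 and 3.25; difference −0.330; SE = √(7.08/300) = 0.154; z = −2.15.
- s = 1.5: V = 80.5, C = 36.3; variances 88.4 and 73.9; difference −0.616; SE = √(162.3/300) = 0.736; z = −0.84.

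The squared ratio of z values gives the equivalent sample-size penalty: (3.53/2.15)² ≈ 2.7 at s = 1.0 and (2.35/0.84)² ≈ 7.9 at s = 1.5.

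Simulated power (2,000 trials per cell):

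| n per group | s | Untransformed change | Log change | Log, baseline-adjusted |
|---|---|---|---|---|
| 300 | 0.5 | 1.00 | 1.00 | 1.00 |
| 300 | 1.0 | 0.62 | 0.94 | 0.97 |
| 300 | 1.5 | 0.19 | 0.66 | 0.74 |
| 100 | 0.5 | 0.93 | 0.98 | 0.99 |
| 100 | 1.0 | 0.28 | 0.53 | 0.60 |
| 100 | 1.5 | 0.08 | 0.29 | 0.32 |

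The normal approximation for the untransformed change gives 0.57 and 0.13 at n = 300, a little below the simulated 0.62 and 0.19. That is unsurprising with heavy tails, and the ordering is the same.

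**False positives.** With no drug effect and no missing data, rates at n = 300 were 4.6% to 5.0%, although the largest 1% of squared deviations carried 18%, 42% and 66% of the sum of squares at s = 0.5, 1.0 and 1.5.

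**Selection.** There was no drug effect on the marker, missingness was set at 20% to 60% and made more likely at a lower follow-up value, and missing values were dropped.

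- Drug does not affect discharge: average log-scale differences were near zero, with false-positive rates of about 3% to 6%.
- Drug shifts discharge by OR 1.65, n = 300: the log-scale difference was +0.010 to +0.037, with false-positive rates of about 4% to 7%.
- A separate illustration with about 19% absent on placebo and 25% to 28% on active gave +0.03 to +0.05. Using the Day 3 values brought this to about 0.00 to 0.015.

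A bias of 0.01 to 0.05 log units is an apparent excess of 1% to 5% (exp(0.01) = 1.010, exp(0.05) = 1.051), or 4% to 22% of the size of a true 20% reduction (0.01/0.223 and 0.05/0.223). Neither the log scale nor baseline adjustment removes it. Where missingness followed underlying severity (s = 1.5, n = 300, 40% missing), log change was off by −0.004 and the baseline-adjusted version by +0.032.

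**The case against.** A reader might infer that outliers and early discharge, rather than the drug, would determine these results. The documents do not support that. Outliers cost precision and leave the false-positive rate at about 5%. Discharge biases the comparison only if the drug changes who can be sampled, and then only slightly; deaths could offset it.

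Other objections stand in part:

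- The SAP is silent on scale, so untransformed analysis is an inference. A difference in means could also be taken on logs. The silence is itself a gap.
- No Day 5 analysis is described. That Day 1 and Day 3 values go unused is inferred from a single change with no day named.
- The SAP's table of oxygen-free days cannot supply the missingness rate. Having 22 or more such days is not the same as discharge by Day 5: someone sent home on oxygen is absent but has few, while an oxygen-free inpatient can still be sampled.
- The power figures describe tests the SAP will not run. They should be read as interval width.
- Six of the eight markers are renin-angiotensin markers that the AngioNECTAR plan may govern. SAP 3.4 still lists them under linear regression, and nothing in SAP 1.1 suggests that plan covers troponin or NT-proBNP.
- Protocol 8.11 lets exploratory analyses be specified later, before execution. That permits the fix; it does not make the stated method better.

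SAP 7.1.1 and 7.1.2 use likelihood handling for missing outcomes, but that contrast adds little here. With one outcome per participant, a wholly missing value carries no likelihood information either. The gain comes from bringing in the earlier samples.

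**Conclusion.** The point holds as a worthwhile, inexpensive improvement. The main reason is precision and prespecification; selection is secondary. If the markers are strongly skewed (log-SD 1.0 to 1.5), an untransformed mean difference loses the equivalent of roughly 2.7 to 7.9 times the sample size. At log-SD 0.5 with 300 per group, power is unaffected. Dropping missing values adds a bias of about 0.01 to 0.05 log units towards apparent harm, and only if the drug alters who remains to be sampled.

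All of this rests on assumed skewness, correlation and missingness, because the documents give none of them. The outcomes are exploratory and untested, so no efficacy conclusion depends on them.

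**What to change.** In SAP 3.4 and 7.1.3:

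1. Analyse troponin and NT-proBNP on the log scale, adjust for the log baseline value as well as the existing covariates, and report geometric mean ratios with 95% credible intervals.
2. Do the same for the renin-angiotensin markers unless the AngioNECTAR SAP governs them, and state which plan does.
3. Fit one repeated-measures model per marker to all scheduled post-baseline samples, so that participants discharged early contribute their earlier values.
4. Name the contrast day before unblinding. The choice of day is for the study team.
5. State what will be done if the residual diagnostics fail.

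The cost is SAP wording and some code, with no new samples. The downsides are that results become ratios rather than assay units, and that the model still assumes missing at random, so selection is reduced and not eliminated.

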7.1.4 Key Secondary Outcome Testing Procedure

A fixed-sequence testing approach will be used to preserve the type-I error rate across tests of the primary and key secondary outcomes. The key secondary outcomes will be tested in the specified order (see *Secondary Outcomes*). This approach provides strong control of the

familywise type-I error rate for the family of primary and key secondary outcomes. No other formal hypothesis tests will be made regarding the secondary, exploratory, or safety outcomes.

All key secondary outcomes use Bayesian logistic regression with a flat prior. Thus, the log odds ratio estimate is also a maximum likelihood estimate (MLE). At the final analysis (only) for each arm and key secondary outcome, efficacy will be indicated using a one-sided likelihood-based Wald test, to ensure a type-I error probability of 2.5% for each test. Specifically, a one-sided test of the null hypothesis ($\log OR = 0$) will be computed by approximating the asymptotic distribution of the MLE under the null hypothesis: a Gaussian distribution with mean zero and variance equal to the inverse observed Fisher information. For descriptive purposes, evidence for efficacy will also be quantified using the posterior probability that the efficacy odds ratio is greater than one (i.e., treatment is associated with greater odds of a favorable outcome). This is denoted the “posterior probability for efficacy” or $P(OR > 1|Data)$, where OR represents the odds ratio, and Data represents the mITT analysis dataset.

7.2 Analysis of Safety, Adherence, and Retention Outcomes for DSMB Review

Monitoring and reporting of safety events will be conducted continuously as described in the Data and Safety Monitoring Plan. Records will undergo monitoring for a two-week period (at minimum) prior to interim analysis for inferiority or futility. However, all records, regardless of monitoring status, will be used in enrollment, demographic, and safety summaries for DSMB safety reporting. Agent-specific safety and toxicity endpoints (if any) are detailed in that therapy’s appendix. The frequencies of PSESEs, adverse events, mortality, and other safety endpoints will be reported. Screening, enrollment, withdrawal, loss-to-follow-up, mortality, study completion, hospitalization status and discharge location will be summarized in a similar manner. All safety-related protocol violations will be listed in the DSMB report. Receipt of planned therapy and adverse events will be recorded on case report forms and monitored continuously. Study drug stoppages and adverse events will be summarized and reported to the DSMB.

8 DATA FLOW, SHARING, AND ARCHIVING

8.1 Requests for secondary use of the data

Requests for secondary use of study data must adhere to review, approval, and provision processes developed by ACTIV 4 Host Tissue leadership and must comply with all applicable rules and regulations. All study data will be de-identified prior to sharing for secondary use.

8.2 Data flow for final and interim analyses

All data necessary for interim analyses, final analyses, and DSMB reporting will be exported from the EDC using the REDCap API. A custom R script will be used to both export the data and perform the interim analyses.

8.3 Archival data model

Data will remain in the production database. At the time of data locking, all users will be moved to read only access or removed, or as specified in the Data Management Plan.

8.4 Final analysis procedure

Once a study arm has completed enrollment, follow-up, and monitoring for all participants, all records that contribute to final analyses will be locked. Final analysis will be executed promptly after data lock, regardless of the status of other study arms. Blinded personnel will remain

blinded to the active/placebo status for individual participants until all arms that share blinded information with the completed arm have also been completed and their records locked. Final analyses will be executed by unblinded personnel only. Reporting of final analyses should avoid revealing the blinded treatment assignment for individual participants.

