### **16.4 21 CFR Part 11 Compliance**

#### **16.4.1 Record locking**

This trial will utilize the REDCap record-locking feature, that will allow the users to lock a participant record. A complete audit trail of the locked records will be kept in the data instrument's history log. Users will receive a prompt when locking an entire record. They will be asked to review a PDF copy of the entire record to confirm it is the correct record and/or file. Once the PDF has been reviewed and confirmed, the record will be locked. All records that are locked using record-level locking will have a duplicate copy of the Portable Document Format (PDF) file automatically stored on a secure file server outside of REDCap. The record-locking feature complies with all the requirements described in 21 CFR Part 11 for FDA trials and has been validated at VUMC.

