2.3 Randomization

Participants are randomized individually at enrollment using a central electronic system. The permuted block method, with stratification by study site and study arm eligibility is used to generate treatment assignments. An eligibility stratum is the collection of study arms for which a participant is eligible. Stratification by site ensures balance across the active and pooled placebo comparator groups at regular enrollment intervals at each site, thus mitigating the impact of site heterogeneity on assessments of treatment effect. Each block contains a multiple of $m(m+1)$ assignments, where m is the number of study arms in the corresponding eligibility stratum. Within each block there are an equal number of allocations across study arms and, for each study arm, there are m active and 1 placebo assignments. For example, in the TXA127 and TRV027 eligibility stratum, each block consists of the following allocations, or multiples thereof:

Study Arm	Placebo/Active
TXA127	Active
TXA127	Active
TXA127	Placebo
TRV027	Active
TRV027	Active
TRV027	Placebo

Thus, within each block, assignments are balanced across study arms, and the active assignments are balanced with the pooled placebo assignments. The block size multiple is either 1 or 2, selected uniformly at random for each block.

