2.4 Blinding

For organizational purposes, the randomized assignment comprises two distinct pieces of information: 1) study arm, and 2) active vs. placebo assignment. The study arm is not blinded, whereas the active/placebo assignment is blinded from participants and investigators (other than unblinded personnel as required for study operations, data quality/analysis, and safety). Blinding will remain in place until all participants have completed the study, all data quality monitoring is complete, and the database is locked.

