4 ANALYSIS DATASETS

For each study arm, the following analysis datasets will be produced using records for participants that were assigned to the active drug group and placebo participants that were *eligible* for the active drug group at the time of randomization:

Modified intention-to-treat dataset: The mITT analysis dataset will include all randomized participants grouped by study arm and active/placebo assignment at randomization, regardless of subsequent compliance or protocol violations, with the following exceptions: 1. Participants who have not received the study drug assigned at randomization will be excluded. 2. Participants who were randomized and later found to be ineligible based on assessments initiated prior to randomization will be excluded. All statistical analyses will be implemented using mITT dataset unless otherwise explicitly specified in this statistical analysis plan.

Intention-to-treat dataset: The intention-to-treat (ITT) analysis dataset will consist of all randomized participants grouped by study arm and active/placebo assignment at randomization regardless of subsequent compliance or protocol violations.

Safety dataset: The safety analysis dataset will consist of all participants grouped by the drug(s) received.

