6 ANALYSIS OF THE PRIMARY OUTCOME

The effect of the active drug versus placebo will be quantified using an odds ratio – the primary estimand – which quantifies the treatment effect on the odds of greater oxygen-free days at day 28. Based on the behavior of similar outcomes in prior trials,²⁻⁶ we anticipate the distribution of the primary outcome to be irregular, with peaks around -1 to 0 and between 22 and 28 days. Thus, we will use a flexible semi-parametric approach for the primary outcome analysis. Estimation and inferences about the odds ratio will be made using Bayesian proportional odds (PO) logistic regression methods, adjusting for the active drug vs placebo indicator variable, age group (18-30, 31-65, >65 years), sex at birth, and WHO COVID ordinal outcome score at baseline (4, 5, and 6-7).⁷ Evidence for efficacy will be quantified using the posterior probability that the active drug versus placebo odds ratio is greater than one (i.e., treatment is associated with greater oxygen free days at day 28). This is denoted the “efficacy probability” or $P(\text{OR} > 1 | \text{Data})$, where OR represents the odds ratio, and Data represents the mITT analysis dataset. The “inferiority/harm probability” is defined as $P(\text{OR} \leq 1 | \text{Data})$. The primary analysis will be implemented separately for each study arm, where the placebo comparator group will consist of placebo participants that were eligible for the corresponding study arm at randomization, regardless of the study arm assigned. The primary and supplementary estimates will be presented with 95% credible intervals.

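### In arms still running, the SAP 8.4 lock for a completed arm covers placebo records only, so lock status can reveal assignment unless it is hidden from blinded staff

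*SAP*

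**What the plan says.** SAP 8.4 triggers locking arm by arm: "Once a study arm has completed enrollment, follow-up, and monitoring for all participants, all records that contribute to final analyses will be locked". It does not wait for the rest of the platform: "Final analysis will be executed promptly after data lock, regardless of the status of other study arms".

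Two other sections define which records contribute. SAP 4 begins: "For each study arm, the following analysis datasets will be produced using records for participants that were assigned to the active drug group and" then adds the placebo participants who could have been allocated to that drug. SAP 6 describes the comparator as "placebo participants that were eligible for the corresponding study arm at randomization, regardless of the study arm assigned".

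On blinding, SAP 2.4 states: "The study arm is not blinded, whereas the active/placebo assignment is blinded from participants and investigators". SAP 8.4 itself requires blinded personnel to remain unaware of individual assignments "until all arms that share blinded information with the completed arm have also been completed and their records locked".

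On the mechanism, Protocol 16.4.1 says: "This trial will utilize the REDCap record-locking feature, that will allow the users to lock a participant record". It adds that users are prompted to check a PDF copy and that locked records have an audit trail in the history log. SAP 8.3 provides for read-only access or removal of users at lock, or for whatever the Data Management Plan specifies. That plan is not among the documents.

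**The concern.** The lock set depends on treatment assignment. Take a finished arm A and a running arm B. A's final analysis uses A's active patients and all placebo patients eligible for A. B's active patients do not enter it, but some of B's placebo patients do. Following the stated rule therefore locks placebo records in B and leaves active records from the same strata open. Anyone who sees the lock, or the list of records to be locked, and knows the open study-arm label can read off assignments that SAP 8.4 says must stay hidden.

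Two things are at stake in arm B. The first is knowledge of individual assignments while the arm is still enrolling or being cleaned; Protocol 15 has unmasked statisticians conceal by-group information from the investigator team. The second is asymmetric handling. Residual data queries, adverse event review and decisions to drop a patient from the mITT set as ineligible could continue in records recognisable as active, while the matching placebo records are frozen.

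Arms finishing at different times is part of the design. Arms may be added or stopped (Protocol 5.1), and by the SAP's own simulation an arm halts early for inferiority 8.6% of the time under the null (SAP 6.6).

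**Working it through.** **Inputs.** SAP 2.3: each block is a multiple of m(m+1) assignments, where m is the number of arms in the eligibility stratum, and "for each study arm, there are m active and 1 placebo assignments". SAP 4 and 6: contributing records as described above. SAP 6.6: about 300 active patients per arm.

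**Step 1: reproduce the plan's block.** For m = 2, m(m+1) = 2 × 3 = 6, with 2 active and 1 placebo in each arm. This matches the TXA127/TRV027 example in SAP 2.3. For m = 3 the block is 3 × 4 = 12, with 3 active and 1 placebo per arm.

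**Step 2: apply the lock set when TXA127 finishes, per block.**

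| Stratum | Arm | Locked | Unlocked |
|---|---|---|---|
| m = 2 | TXA127 (finished) | 2 active, 1 placebo | none |
| m = 2 | TRV027 (running) | 1 placebo | 2 active |
| m = 3 | TXA127 (finished) | 3 active, 1 placebo | none |
| m = 3 | each running arm | 1 placebo | 3 active |

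In the finished arm everything is locked, so the lock tells staff nothing. In a running arm, the probability of placebo before the lock is 1/(m+1), that is 1/3 or 1/4. Given a lock it is 1. Within the shared stratum, the probability of active given no lock goes from m/(m+1), that is 2/3 or 3/4, to 1.

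**Step 3: scale, with an assumed overlap.** Suppose B has 300 active patients. A share f of them was randomised in the two-arm stratum with A, and the rest 1:1 in a B-only stratum. Then:

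- B placebo locked = 300f/2 = 150f
- B placebo left unlocked = 300(1 − f)
- Assignments exposed = 300f active + 150f placebo = 450f
- P(active given unlocked), all of B = 300 / [300 + 300(1 − f)]

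| f | B placebo locked | B placebo unlocked | Assignments exposed | P(active given unlocked), all of B |
|---|---|---|---|---|
| 1.00 | 150 | 0 | 450 | 1.00 |
| 0.75 | 112.5 | 75 | 337.5 | 0.80 |
| 0.50 | 75 | 150 | 225 | 0.67 |
| 0.25 | 37.5 | 225 | 112.5 | 0.57 |

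P(placebo given locked) is 1 in every row. The documents do not give f.

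**Step 4: what each inference requires.** Reading a locked record as placebo needs only the study-arm label, which is open. Reading an unlocked record as active also needs to be told, or to work out, that the patient was eligible for both arms.

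**The case against.** The best reply is that SAP 8.4 says what must be locked, not that nothing else may be. Its later clause about other arms' records being locked fixes when unblinding may occur, not when B's individual records may first be locked. Protocol 16.4.1 does not tie locking to arm completion, so B's active records could already be locked. Section 8.4 also states the blinding requirement, so a lock that revealed treatment would breach the SAP, and the unseen Data Management Plan may hide lock status. This stands as a limit on certainty. It does not clear the rule: no sentence has B's active records locked with A's, and neither document describes masking. The SAP 8.3 default of read-only access or removal cannot apply to every user while other arms are still entering data.

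The reply also limits the harm. Patients eligible for A were randomised while A was open (Protocol 6.7), and A locks only after its follow-up and monitoring are complete. Their counterparts in B are therefore largely past day 28, and what remains open is mostly late correction and review. The mITT exclusion for ineligibility is confined to assessments initiated before randomisation (SAP 4).

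Some stronger readings are tempting but unsupported:

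- *Only active records stay editable in the running arm.* Placebo patients outside the shared strata also stay unlocked; at f = 0.50 there are 150 of them.
- *12% of 300, or 36, active records have a primary outcome still open to change.* The 12% in SAP 6.6 was observed in participants who had already completed follow-up and monitoring. It is residual missingness, not a queue of pending data.
- *Blinded staff could compute B's treatment effect.* That needs pooled outcomes across sites as well as lock status. The documents do not say blinded staff hold both, and Protocol 12.4 keeps data access to as few people as necessary.
- *The monitoring of records before analyses (SAP 6.3) has the same fault.* Nothing there selects records by treatment.

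**Conclusion.** The point holds in a conditional form. As written, the lock rule for a completed arm picks out placebo records only in any running arm that shares eligibility strata with it. This works against the blinding requirement in the same section. A reader might infer that the blind is certainly broken; the documents do not show that. It is broken if blinded users can see lock status or the lock list, and if B's active records from the shared strata are not locked at the same time for some other reason. The record-level lock operated by users makes the first condition plausible, and nothing in either document prevents it.

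Where those conditions hold, every shared placebo patient in the running arm is identified, and shared active patients are identified by elimination. The 450 figure is the upper bound for two fully overlapping arms with 300 active patients in the running arm, not an expectation. The effect on the primary odds ratio cannot be quantified from the documents and is probably limited, because most shared patients have finished day-28 follow-up. The correction should be made because the exposure is avoidable at almost no cost.

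**What to change.** Amend SAP 8.4 so that the lock does not depend on assignment, in one of two ways:

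1. When an arm completes, lock at the same time the records of all participants whose eligibility group included that arm, whatever their study arm and whether active or placebo.
2. Apply no lock visible to blinded users in running arms. The unblinded statistician freezes a dated export as the analysis dataset for the completed arm.

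Under either option, state that no lock list derived from treatment assignment goes to blinded staff.

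The cost is one paragraph of SAP text. Option 1 requires the shared patients in running arms to be cleaned by the same date, which is feasible because they were randomised while the completed arm was open. Option 2 requires storing one export; SAP 8.2 already plans exports from the data system for interim and final analyses. Neither needs extra patients, visits or staff.
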